Attention placebo control. The attention placebo control arm will receive a 9-minute video clip of a video on another topic. Attention placebo controls should mimic the theoretically inactive components of the active treatment under study, while having none of the theoretically active components of that intervention (Freedland, <http://europepmc.org/articles/pmc3091006>). The attention placebo control video was matched to the active treatment video in length, pace, tone, narrative structure, visual imagery (daily life in a local community), and language (Zulu with English subtitles), but it was lacking specifically in the active intervention content (i.e. information about longevity gains with ART). The video selected was about the challenges of raising children in households where the household head has a physical disability. It was filmed in a nearby community that was not in the surveillance area. The video was found online and we received permission to use this video from its creators. The video was edited to be 9 minutes and to contain no discussion of HIV treatment and longevity. We note that in clinical behavioral intervention studies, attention placebo controls should induce the same expectation of therapeutic benefit as the treatment. Our study was not conducted in a clinical setting, and neither the active treatment nor the attention placebo control was presented as a therapeutic intervention.

Pure control. The pure control arm will view no video and will simply continue with the baseline survey.

A8.2. Randomization procedures

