The researchers will be blinded to the randomization status of participants throughout the data collection, extraction, and cleaning/quality control process, up until the date when randomized assignments are unmasked. To maintain blinding of treatment assignments vis-à-vis the research team during the study, we will use the following procedures:

- Treatment assignment will be stored as a hidden field in the REDCap database. I.e. during the baseline survey it will generate a pop-up message telling the interviewer to show the participant the active treatment video, active control video, or no video, however this field will not be visible to anyone on the research team.
- The treatment assignment field will not be exported during routine quality control procedures.
- Treatment assignment will be extracted along with study ID into its own table and will not be merged with any of the other data until randomization is unblinded.
- Randomization will be unblinded only after the final Pre-Analysis Plan is posted to www.clinicaltrials.gov. In developing our pre-analysis plan, we conducted some descriptive analysis of the blinded baseline pre-intervention survey data. Additionally, we monitored overall levels of uptake of the HIV testing voucher and job search training workshop in order to determine potential statistical power with these outcomes. For guidance on using baseline data to inform Pre-Analysis Plans, see Olken (2015).
- We will submit an update to our clinicaltrials.gov study profile after treatment assignment is unblinded, noting the date when we have done so.

As this is a short (4-month) pilot study and the intervention is minimal risk, we do not have a DSMB and do not have stopping rules for the trial based on preliminary analysis of efficacy.

A9. Baseline interview and intervention

The baseline survey visit is designed to take about 1.5 hours, and consists of the following sub-components:

A9.0. Recruitment and Informed Consent

Potential respondents will be recruited via visits to their homesteads. Permission will be obtained from the head of household to enter and to speak to the sampled participant. The study will be described and participants will provide written informed consent to participate in the study, including the baseline visit, a follow-up visit, and permission to link with demographic surveillance data. See Appendix B for the approved consent form.

A9.1. Survey module

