First, we will conduct a survey questionnaire with young adults ages 18 to 25 to learn about their survival expectations, perceptions of HIV risks and treatment, future-oriented behaviors such as smoking, alcohol use, HIV risk behaviors, savings, locus of control, mental health, time and risk preference, and life satisfaction.

A9.2. Video intervention

All study participants will have been randomly assigned *ex ante* to one of the three study arms: active treatment, attention placebo control, and pure control. Both interview participants and interviewers will be blinded to treatment assignment during the baseline survey and treatment arm will only be revealed at the time when the video will be shown. During the baseline survey, randomization status will be revealed, and the participant will be shown the video corresponding to their treatment arm, or will not be shown a video if randomized to pure control.

A9.3. Re-survey module

Immediately after the video intervention, all study participants will be asked a brief subset of the survey module questions to re-measure survival expectations, locus of control, and life satisfaction. This step will aim to assess the immediate impact of the video intervention on beliefs.

A9.4. Rapid assessment behaviors

Following the baseline survey participants will be offered several behavioral prompts:

HIV Testing Voucher. Immediately after the re-survey module, we will offer participants a voucher for free HIV testing at a local pharmacy. We will provide respondents with information about the benefits of testing, the benefits of HIV treatment, and the availability of free testing and treatment in public sector facilities. We will then offer a voucher for free HIV testing in local private pharmacies. Participants will be provided R10 with the voucher, to subsidize transport. The cost of testing in these facilities is usually R100, but will be available to people for free during a time-limited period if they bring the voucher. At the end of the study, we will visit the pharmacies to collect the vouchers that have been redeemed and we will pay the pharmacies for the cost of the testing provided. We will record the voucher numbers redeemed, as an indicator of participation in HIV testing, but will not record any information about participants' test results. This information will be stated clearly on the voucher.

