Definition: Subjective life expectancy is defined as the area under the subjective survival curve. Respondents will be asked about the chances of surviving to age 30, 40, ..., 80 years. We will linearly interpolate the responses beginning at their current age and ending at 80 years. We will then calculate the area under this curve, which we define as subjective life expectancy (number of years expected to live between current age and age 80). Our primary outcome for beliefs will be the change in subjective life expectancy between baseline (pre-intervention) and follow-up (at 2 months). We will also assess change in subjective life expectancy between baseline and immediate post-intervention assessment as a secondary outcome.

[Time Frame: 2 months]

4. Positive attitudes towards HIV and HIV treatment (at 2 months)

Definition: Immediately after the intervention and at 2 months, we ask participants whether they strongly disagree, disagree, agree, or strongly agree with a series of statements regarding attitudes towards HIV and HIV treatment. As a primary outcome, we will assess differences in a composite index of 12 of these measures, comparing attitudes between treatment arms at 2 months. We will assign points (1=strongly disagree, 2=disagree, 3=agree, 4=strongly agree) based on responses, we will sum over the following items, and we will construct a z-score based on the mean and standard deviation in the baseline data. "Reverse code" denotes that the variable will be scored (4=strongly disagree, 3=disagree, 2=agree, 1=strongly agree). We will also assess differences immediately after the intervention as a

secondary outcome. Note: the attitudes questions are asked after the intervention. There is no baseline.
 [Time Frame: 2 months]

ITEM	REVERSE CODE?
If I were HIV infected, I could have children and a family	
If I were HIV infected, it would be difficult to find a romantic partner	X
If I were HIV infected, I could still do all the activities I enjoy	
If I were HIV infected, it would make it harder to get and keep a job	X
If I were HIV infected, it would change my career plans	X
If I were HIV infected, I could expect to live to pension age (age 60)	
If I were HIV infected, I could expect to live long enough to see my children grow up and to meet my grandchildren	
I am scared to find out my HIV status	X
If I were HIV infected, it would be hard to start ARVs (HIV treatment)	X

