If I were HIV infected, I would want to start ARVs (HIV treatment) as soon as possible, even if I didn't feel sick	
If I were HIV infected, I would prefer to wait as long as possible to start ARVs	X
If I were HIV infected, I would choose not to start ARVs.	X

B1.2 Secondary Outcome Measures

Behaviors

Attendance at job search skills workshop

Definition: Participants will be invited to a job search skills workshop; workshops were held in nearby locations 1-3 weeks after each survey week-block; attendance will be measured as a binary indicator

[Time Frame: 2 weeks]

Condoms purchased

Definition: Participants will be offered the opportunity to purchase discount condoms; the number purchased will be assessed; range 0 to 10 condoms
[Time Frame: Baseline survey]

Savings allocated

Definition: Participants will be offered the opportunity to allocate a portion of their participation incentive to a savings device (lock box); amount allocated will be assessed; range 0 to 100 Rand
[Time Frame: Baseline survey]

Savings at 2-month follow-up

Definition: At follow-up, participants are asked if they still have the savings tin and if they have added money to the tin since baseline. They are then asked to estimate the total savings inside today or on the date when they opened it. If they still have the tin on hand, we then open it, count their savings, and provide them with a new tin to continue saving. We will define 2-month savings in two ways: first, as the amount the participants self-report they have in the tin on the follow-up interview date or, if they no longer have the tin, on the last day they had it; and second, as the amount we validate by opening the tin, with zeroes imputed if the tin is not available or money used.

[Time Frame: 2-months]

Use of HIV testing voucher

Definition: Participants will be provided with a voucher for free HIV testing at a local service provider (we partnered with two local pharmacies that provided government certified HIV testing services); use of voucher will be assessed by obtaining voucher numbers from the service provider

[Time Frame: 1 month]

Uptake of HIV testing in the AHRI surveillance

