Definition: change from baseline to 2-month follow-up in an index of questions on locus of control. Research in economics that investigates the effect of perceptions on human capital formation (Bernard et al. 2014, Heckman and Kautz 2012, Heckman et al. 2006) commonly uses the Internality, Powerful Others, and Chance (IPC) scale to explore three separate components of locus of control (Levenson 1981, [20]). We use a subset of Levenson's scale, two questions per component, for each component of the IPC scale. We score respondents with a 1 if the strongly disagree and a 4 if the strongly agree. To create a composite score for each component of the scale, we then combine the total per question. A score of 8 on the internality scale implies that an individual feels the highest level of control over their lives. Based on our formative qualitative research, we also added a question on the role of external forces, e.g. God, witchcraft, etc. To reduce the likelihood of false positives, we create an index of all questions related to locus of control by aggregating scores (reverse coding such that higher score for all questions reflect greater perceptions of control). We will construct a z-score by subtracting the baseline mean and dividing by the baseline standard deviation. If we observe statistical significance at the index level, we then will investigate treatment effects by sub-scale and individual components.

ITEM	SUB-SCALE	REVERSE
I can mostly determine what will happen in my life	Internality	
My life is determined by my own actions	Internality	
I feel like what happens in my life is mostly determined by powerful people, including parents, friends, and politicians.	Powerful others	X
People like myself have very little chance of protecting our personal interests when they conflict with those of more powerful people	Powerful others	X
I feel like what happens in my life is mostly determined by external forces, such as god, the ancestors, or witchcraft.	External forces	X
To a great extent my life is controlled by accidental/chance happenings, luck, or fate	Chance	X
It is not always wise for me to plan too far ahead because many things turn out to be a matter of good or bad fortune	Chance	X

Change in health-related locus of control

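### Does primary outcome 4 (attitudes) lack a usable z-score reference because it has no baseline measurement?

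*Combined protocol and SAP*

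**What the plan says.** B1.1 defines primary outcome 4 as the sum of 12 attitude items, each scored 1 to 4 with some items reversed. The arms are compared at 2 months; the comparison just after the video is secondary. On scaling, the definition says "we will sum over the following items, and we will construct a z-score based on the mean and standard deviation in the baseline data". Its closing note says "the attitudes questions are asked after the intervention. There is no baseline".

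The document uses the word baseline in two senses:

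- **Before the video.** Primary outcome 3, immediately above, is the "change in subjective life expectancy between baseline (pre-intervention) and follow-up (at 2 months".
- **The whole first visit, video included.** A9 opens with "The baseline survey visit is designed to take about 1.5 hours, and consists of the following sub-components", and the video and the offers made after it are among those parts. A9.2 says "During the baseline survey, randomization status will be revealed, and the participant will be shown the video corresponding to their treatment arm". A8.1 says "The pure control arm will view no video and will simply continue with the baseline survey". In B1.2, condom purchase and savings allocation both follow the video, yet both carry the label "Time Frame: Baseline survey".

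The locus-of-control index in B1.2 uses the same scaling rule: "We will construct a z-score by subtracting the baseline mean and dividing by the baseline standard deviation". The health locus-of-control and mental health indices do likewise. Those three are change scores with a pre-video measure, so the rule works for them without comment.

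**The concern.** Within one definition, a primary outcome is standardised on data that the definition then appears to say were never collected. If baseline means before the video, as it does for outcome 3, the instruction cannot be carried out. The wording looks carried over from the change-score indices.

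If baseline means the first visit, the reference is a set of post-video answers, about half of them from people who have just seen the active video. The text does not confirm this reading, and it does not say whether all arms or only the controls form the reference.

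This is one of four primary outcomes. At stake is the unit of its reported effect and 95% CI, and so whether that effect can be set against the 0.26 SD on which the trial was sized. The z-scored arm means that B4 asks for would also move with the reference mean.

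**Working it through.** **Inputs.** Target 450 participants, 80% power and a detectable difference of 0.26 SD (A7). Allocation for the primary contrast is 50:50 (B2), so 225 against 225. Two-sided 5% is assumed, in line with the 95% CIs in B4. Clustering and dropout are left out. The documents give no SD for the attitudes score.

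**1. The plan's own figure.** Detectable difference = (1.960 + 0.842) × √(2/225) = 2.802 × 0.0943 = 0.264 SD, which agrees with the stated 0.26. Power at exactly 0.26 is 78.7%.

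**2. Effect of the reference on the test.** Let Y be the raw sum and z = (Y − m)/s, with one m and one s for everybody. In the B4 regression:

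- m goes into the intercept and cancels from the arm difference;
- the coefficient becomes b/s and its clustered standard error becomes SE/s;
- t = (b/s)/(SE/s) = b/SE, so t and p do not depend on m or s;
- an arm mean becomes (mean of Y − m)/s, so its location does depend on m.

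**3. Numerical check.** One simulated data set had 450 people in 300 households, 12 items scored 1 to 4, week-block indicators and household-clustered errors. Its values are illustrative.

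| Scaling of the 2-month sum | Reference SD | Effect | t | p |
|---|---|---|---|---|
| Raw points | – | 1.759 | 3.466 | 0.00053 |
| First visit, all arms | 5.258 | 0.335 | 3.466 | 0.00053 |
| First visit, controls | 5.335 | 0.330 | 3.466 | 0.00053 |
| 2 months, all arms | 5.101 | 0.345 | 3.466 | 0.00053 |
| 2 months, controls | 5.157 | 0.341 | 3.466 | 0.00053 |

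**4. All arms or controls only.** Assume equal within-arm SDs and the same 0.26 shift at both time points. The pooled SD is √(1 + 0.26²/4) = 1.0084 control SDs.

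- Control unit: 0.260, with CI 0.26 ± 1.96 × 0.0943 = 0.075 to 0.445.
- Pooled unit: 0.26/1.0084 = 0.258, with CI 0.075 to 0.441, which is 0.8% smaller.
- At a shift of 0.5 SD the pooled SD is √(1 + 0.5²/4) = 1.031 control SDs, so 3.1% larger.

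**5. First visit or 2 months.** This choice could matter more, and the documents do not allow it to be sized. Over an assumed range for the ratio of reference SD to 2-month SD:

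- ratio 0.8: 0.26/0.8 = 0.325;
- ratio 1.0: 0.260;
- ratio 1.2: 0.26/1.2 = 0.217.

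The CI limits are divided by the same ratio, so an interval cannot gain or lose zero.

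**6. Precision of the reference SD.** The relative standard error is 1/√(2(n − 1)): 3.3% for n = 450 and 4.7% for n = 225. Both exceed the 0.8% in step 4.

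**The case for a change.** The strongest case for changing the text runs as follows. The plan was posted as final on 17 September 2018, with unblinding the next day (A12), so an analyst would fix the unit after seeing the arms. The first-visit reading also sits badly with B3 and B4(c). B3 checks balance on outcomes measured at baseline, and B4(c) adjusts for variables that differ at p < 0.1. If post-video attitudes counted as baseline, the plan could end up adjusting for a consequence of treatment. One sentence naming the reference, with the raw difference reported alongside (range 12 to 48), would cost almost nothing.

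Part of this stands. The reference is ambiguous, no other section names it, and the time-point choice cannot be shown to be small. The openness also reaches the z-scored arm means as well as the effect and CI.

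The rest carries less weight:

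- **Workable reading.** The closing note tells the reader that no pre-video measure exists, which explains why this outcome is compared between arms and not as a change. It does not say that the first visit holds no attitude data. The definition itself places the items straight after the intervention, although the short topic list in A9.3 omits them.
- **The balance route.** The same note keeps attitudes out of the balance table, so the risk of adjusting for them does not arise in practice.
- **All arms or controls.** The rule names no subset, so all participants is its plain meaning. A control-only SD is a preference, and its sampling error (4.7%) is larger than the gap it would close (0.8%).
- **Choosing after unblinding.** The choice cannot alter a p-value or whether a CI excludes zero.

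**Conclusion.** No change to the plan is needed. The wording is loose: it cites baseline data for an outcome with no pre-video measure. An analyst would settle it sensibly, most likely with the first-visit answers from all arms, and would state the reference used.

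The consequence is confined to the SD unit of one reported effect and its CI, and to the location of the z-scored arm means. For a 0.26 SD effect, the choice between pooled and control SD is worth about 0.8%. The choice of time point is worth 0.217 to 0.325 over an assumed SD ratio of 1.2 to 0.8. The raw sum, t, p, power and the conclusion are the same throughout, and no threshold or decision rule in the plan uses the SD unit of this outcome.

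This rests on one common mean and SD being applied to everyone; standardising each arm separately would break it, and nothing in the plan suggests that. The 0.8% also assumes equal within-arm SDs and the same effect at both time points.

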HIV testing. We will test the null hypothesis that the video intervention will have no effect on uptake of HIV testing as measured via either use of the HIV testing voucher or participation in home-based HIV testing in the AHRI surveillance visit occurring about six weeks after baseline.

Job search skills workshop. We will test the null hypothesis that the video intervention will have no effect on uptake of a job search skills workshop occurring 1-3 weeks after the baseline interview that all participants will be invited to.

Savings. We will test the null hypothesis that the video intervention will have no effect on the amount (out of 100 Rand) allocated to the savings tin offered at the end of the baseline visit.

Additionally, to better understand changes in beliefs and attitudes, we will test the null hypothesis that the video intervention will:

- Have no effect on attitudes towards HIV treatment and its efficacy
- Have no effect on perceptions of survival in the community

- Have no effect on measures of future orientation, locus of control, life satisfaction, and mental health
- Have no effect on beliefs about future education and employment
- Have no effect on attitudes towards the importance of using condoms

Additionally, to better understand changes in self-reported behaviors, we will test the null hypothesis that the video intervention will:

- Have no effect on time use allocated to education or labor supply activities, including job search
- Have no effect on self-reported HIV testing
- Have no effect on self-reported smoking, drinking, seatbelt use
- Have no effect on sexual activity and condom use

Additionally, it is possible that providing information on the benefits of HIV treatment would reduce demand for HIV prevention, a response known as risk compensation. It is also possible that increased optimism about the future would lead to greater demand for HIV prevention. Therefore, we will test the null hypothesis that the video intervention described will:

- Have no effect on demand for HIV prevention, as measured by number of condoms purchased when offered at the end of the baseline survey

Subgroup analyses

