Definition: We will assess changes between baseline and 2-month follow-up in self-reported unprotected sex. Specifically, we will assess number of times a person reported having condomless sex in the last 30 days.

[Time Frame: 2 months]

Change in self-reported current HIV care-seeking

Definition: We will assess change between baseline and 2-month follow-up in a combined self-report measure of whether the respondent either tested for HIV within the last 3 months and whether the respondent is currently taking ARVs.

[Time Frame: 2 months]

Employment, education, and care-seeking outcomes in the AHRI surveillance

Definition: We will assess longer run education, employment, migration, and care-seeking outcomes observed through household proxy report and clinic linkage in the AHRI population-based surveillance platform. Specifically, we will assess whether the respondent is reported to be in school, working, looking for work, or none of the above; whether the respondent is still residing in the surveillance area; and whether the respondent has linked to clinical HIV services.

[Time Frame: 1 year, 2 years]

Attitudes and beliefs

Change in beliefs about life expectancy in the community

Definition: at baseline and at 2-month follow-up, we ask people to consider 20 people their age and gender in the community and to estimate how many they think will be alive at age 30, 40, ... 80. We will construct a measure of perceived community life expectancy by linearly interpolating the responses to these questions (starting at the respondent's age) and computing the area under the curve. This value is the average number of years they expect a demographically similar person in the community to live.

[Time Frame: 2 months]

Change in beliefs about lifetime risk of HIV infection

Definition: change between baseline and 2-month follow-up in the subjective probability (out of 20) of becoming HIV-infected at some point in their life. Although we do not expect that the video will change underlying beliefs about HIV risk; it could change people's willingness to consider these risks, which would be important to know in interpreting our results.

[Time Frame: 2 months]

Change in beliefs about work and schooling

Definition: At baseline and 2-month follow-up we asked respondents about the chances (out of 20) that they would complete different levels of schooling and about the chances they would be employed in the future. We will assess changes in these beliefs.

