Adjusted effect estimates. We will estimate adjusted effect estimates in multivariate linear regression models. Adjustment for covariates in an RCT has three aims[23]:

- (design variables) to obtain appropriate standard errors when conducting stratified or constrained randomization;
- (strong predictors of the outcome) to reduce residual variance in the outcome, leading to smaller standard errors and narrower confidence intervals; and
- (factors with strong baseline imbalance) to eliminate the impact of any imbalances on observed baseline factors, despite randomization

(a) In our adjusted analyses, we will include the following design variables:

- Stratification variables: week block
- Constrained randomization variables: sex, age, whether the person was in school, orphan status, HIV positive status, HIV negative status (unknown is the third category), and household asset quintile

(b) We will include the following variables believed *a priori* to be strong predictors of HIV testing and human capital investment:

- Distance to nearest clinic
- Baseline subjective life expectancy
- Baseline beliefs about lifetime HIV infection risk

(c) Finally, to eliminate imbalances on observables, we will adjust for variables with $p < 0.1$ for the t-test of differences between Arm 1 and Arm 2+3.

B5. Subgroup analyses

The informational intervention is expected to have the greatest impact for individuals with low baseline survival beliefs and for individuals with high baseline beliefs about lifetime chances of contracting HIV.

Perceived likelihood of lifetime HIV infection. The impact of the informational video is likely to vary by baseline perceived risk of lifetime HIV infection. We will assess for linear effect modification of our primary outcomes by perceived lifetime infection risk.

Baseline survival expectations. The impact of the informational video is likely to vary by baseline survival expectations, with the greatest potential shift in beliefs for individuals with previously low survival expectations. We will assess for linear effect modification of our primary outcomes by baseline subjective life expectancy.

Finally, we will assess effect modification by age (continuous, 18-25) and sex of the respondent (M/F).

B6. Robustness checks

We will subject our primary results (Arm 1 vs. Arms 2+3 for primary outcomes) to robustness checks.

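### Condoms purchased has no pre-specified predictor of its own in the adjusted model: baseline sexual behaviour is left out of B4(a) and (b), at a modest and uncertain cost in precision

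*Combined protocol and SAP*

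**What the plan says.** Section A4 raises risk compensation as a possible response to the video and attaches one null hypothesis to it: "Have no effect on demand for HIV prevention, as measured by number of condoms purchased when offered at the end of the baseline survey". Section A9.4 describes the measurement. After the video and the voucher offer, each participant receives R20 and may spend it on up to ten condoms, and the study records how many are bought. B1.2 lists the result as a secondary outcome: "Participants will be offered the opportunity to purchase discount condoms; the number purchased will be assessed; range 0 to 10 condoms".

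Section B4 sets one adjustment scheme for all outcomes and reports three estimates: crude, design-adjusted and fully adjusted. It gives the purpose of the predictor group as "strong predictors of the outcome) to reduce residual variance in the outcome, leading to smaller standard errors and narrower confidence intervals". The covariates come from three sources:

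- B4(a): week block, then "Constrained randomization variables: sex, age, whether the person was in school, orphan status, HIV positive status, HIV negative status" and household asset quintile.
- B4(b): distance to clinic, baseline subjective life expectancy and baseline perceived lifetime HIV risk, believed a priori "to be strong predictors of HIV testing and human capital investment".
- B4(c): any variable with p<0.1 in the Arm 1 versus Arms 2+3 balance test.

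On baseline sexual behaviour, A9.1 says the survey module given before the video covers "future-oriented behaviors such as smoking, alcohol use, HIV risk behaviors, savings, locus of control" and other topics. B1.2 is more specific: "We will assess changes between baseline and 2-month follow-up in self-reported unprotected sex", and then "Specifically, we will assess number of times a person reported having condomless sex in the last 30 days".

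**The concern.** B4 justifies its predictor covariates by how well they explain the outcome being analysed, but the fixed list was picked for other outcomes. Demand for condoms is neither HIV testing nor human capital investment, and an obvious candidate for explaining who buys condoms is recent sexual behaviour. The outcomes defined as change from baseline remove some between-person variation by differencing. Condoms purchased cannot, because it is observed only once.

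At stake is the width of the interval for the one recorded, rather than self-reported, measure of demand for HIV prevention. Section A7 already concedes that this pilot can detect only large effects, so precision that costs nothing is worth taking on a question about a possible unintended effect.

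**Working it through.** **Is the covariate in the model?** B4(a) has no sexual-behaviour item, and neither does B4(b). Baseline condomless sex does belong in the balance table, because B3 includes every secondary outcome measured at baseline. It can therefore enter under B4(c). With a p<0.1 threshold and random allocation, that happens about one time in ten, and it depends on chance imbalance rather than on predictive strength.

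**Is it safe to adjust for?** A9.1 places HIV risk behaviours in the module before the video. A8.3 keeps participant and interviewer blind to assignment until the video. The re-survey after the video (A9.3) covers only survival expectations, locus of control and life satisfaction. A baseline sexual-behaviour item is thus measured before treatment, and adjusting for it introduces no post-treatment bias.

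**The plan's own figure.** Inputs from A7 and A8.2: 450 participants, split 225 versus 225 for Arm 1 against Arms 2+3, and 80% power. Assumption: two-sided alpha of 0.05, which A7 does not state but which fits the 95% intervals in B4.

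- Detectable difference = (1.960 + 0.842) × sqrt(2/225) = 2.802 × 0.0943 = 0.264 SD. The stated 0.26 SD reproduces.
- Power at exactly 0.26 SD is 78.7%.

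Condoms are bought at the baseline visit, so loss to follow-up does not reduce the 450.

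**Effect of adding the covariate.** Let R² be the partial R-squared of baseline sexual behaviour for condoms purchased, given the covariates already in the model. Then:

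- SE factor = sqrt(1 − R²)
- Detectable difference = 0.264 × sqrt(1 − R²)
- Equivalent sample = 450/(1 − R²)

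The documents give no R², so the values below are assumed.

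| Partial R² | SE reduction | Detectable difference (SD) | Power at 0.26 SD | Equivalent N |
|---|---|---|---|---|
| 0 | 0% | 0.264 | 78.7% | 450 |
| 0.02 | 1.0% | 0.261 | 79.6% | 459 |
| 0.05 | 2.5% | 0.257 | 80.8% | 474 |
| 0.10 | 5.1% | 0.251 | 82.8% | 500 |
| 0.20 | 10.6% | 0.236 | 86.9% | 562 |

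The plan clusters standard errors by household but states no design effect. With an assumed design effect of 1.1, the detectable difference is 0.277 SD at R² = 0, 0.263 at 0.10 and 0.248 at 0.20. The proportional reductions do not change.

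**The case against.** **The best covariate may not exist.** The only specific baseline item in the documents is the count of condomless acts. A9.1 speaks generally of HIV risk behaviours, and A4 lists sexual activity and condom use among the self-reported behaviours without naming a baseline question or recall period. A reader might infer that a yes/no item on recent sex is already in hand, but the documents do not show it. The item that is documented may predict poorly, because it is zero both for people having no sex and for consistent condom users, who may be the likeliest buyers. This stands, and it limits the expected gain.

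**The gain is easily overstated.** Suppose 60% are sexually active, active participants buy 4 more condoms, and the within-group SD is 3.5 (all assumed). Between-group variance is 0.6 × 0.4 × 4² = 3.84, so R² = 3.84/(3.84 + 12.25) = 0.24. The SE would fall about 13%, and the equivalent N would be 450/0.761, about 591. That is a marginal R². Sex, age, schooling, HIV status and perceived HIV risk are already in the model, so only the partial R² counts. With a difference of 1 condom on the same assumptions, R² = 0.24/12.49 = 0.02 and the gain is about 1%. This also stands.

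**Footnote b to the B4 results table.** It begins by tying strong predictors to the baseline balance table and then breaks off, at least in the text available. One reading would make baseline condomless sex eligible as a predictor. A broken footnote does not displace the explicit list in B4(b), but the two should be reconciled.

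**A null need not be read as reassurance.** A reader might infer that the plan would treat a null as showing no risk compensation. It does not say so. A4 allows effects in either direction, A7 warns of limited power, and condomless sex and condom attitudes are also examined.

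**This is a preference, not an error.** It is true that no test is invalid and that similar suggestions could be made for other outcomes. What sets this outcome apart is that it has no baseline value, falls outside the stated purpose of the B4(b) list, and carries the risk-compensation hypothesis.

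**Conclusion.** The point holds as a modest efficiency improvement on a secondary outcome. By B4's own rationale, Condoms purchased lacks an outcome-specific predictor, although relevant data are collected before the video. For an assumed partial R-squared of 0.02 to 0.20, the standard error falls by about 1% to 11%. The gain may be negligible if condomless acts are the only usable item.

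A reader might go further and infer that the risk-compensation test is biased or invalid. The documents do not support that: allocation is randomised, the omitted variable precedes treatment, and the crude and adjusted estimates all remain valid comparisons. The primary outcomes and their conclusions are unaffected.

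**What to change.** In B4(b), add one sentence for Condoms purchased: the fully adjusted model also includes the baseline sexual-behaviour items collected before the video, namely recent sexual activity if the questionnaire has it, together with condomless acts in the last 30 days. Keep reporting the crude and design-adjusted estimates for this outcome.

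Complete footnote b to the B4 results table so that it agrees with B4(b) on where strong predictors come from.

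Section A12 puts unblinding one day after posting of the plan. The change therefore belongs in the plan before unblinding. If made later, it should be labelled post hoc.

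The cost is a sentence and a corrected footnote, plus a check of the questionnaire for a recent-sexual-activity item. Nothing new needs to be collected, since the fix uses only items already in the baseline survey.
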